9.2 Adverse Event (AE) Reporting

An adverse event (AE) is any untoward medical occurrence in a patient who is taking part in a research study. In this trial, a pre-existing condition (i.e., a disorder present before the AE reporting period started and noted on the pre-treatment medical history/physical examination form/medical notes) is not to be reported as an AE unless the condition worsens or episodes increase in frequency during the AE-reporting period.

Diagnostic and therapeutic non-invasive and invasive procedures, such as surgery, are not to be reported as AEs. However, the medical condition for which the procedure is performed is to be reported if it meets the definition of an AE. For example, an acute appendicitis that begins during the AE reporting period is to be reported as the AE (serious) and the resulting appendicectomy noted under comments.

If a clinically significant abnormal laboratory value occurs, this abnormality (but not the value itself) should be entered on the adverse event page.

Expected Adverse events include the following:

- Worsening of symptoms of heart failure
- Admission to hospital for acute decompensation of heart failure
- Worsening angina
- Admission to hospital with angina

Each trial subject will be questioned about adverse events at each visit. The investigator will record all directly observed AEs and all AEs spontaneously reported by the trial subject.

The AE reporting period for this trial begins on randomisation, and ends 30 days after the patients' final research clinic appointment.

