[name], Director of York Trials Unit, [name]. [contact], [contact], [contact]

Contents

1. Trial Synopsis	3
2. Background and Rationale	5
3. Aims and Objectives	7
4. Study Design	9
5. Patient Eligibility and Participation	.13
6. Trial Evaluations	16
7. Health Economic Assessment	22
8. Statistical Considerations	23
9. Pharmacovigilance	24
10. Research Governance	27
11. Ethics, Confidentiality and Liability	. 30
12. The Study Team	31
Deferences	21

1. Trial Synopsis

Patients with Chronic Heart Failure (CHF) commonly have significant limiting symptoms despite optimal management. The prevalence and clinical relevance of hypoxaemia in patients with CHF is incompletely understood. Currently, Home Oxygen Therapy (HOT), in various forms, is used commonly despite the absence of evidence of benefit.

The present study seeks to address the uncertainties surrounding home oxygen therapy for patients with chronic heart failure who are still severely symptomatic despite maximally tolerated medical therapy. The study will randomise 450 patients equally to its active treatment arms. These are (a) best medical therapy without oxygen (b) best medical therapy with daytime Long Term Oxygen Therapy (LTOT for at least 15 hours per day in the home, including overnight hours) or (c) best medical therapy with Nocturnal Oxygen Therapy (NOT overnight in the home). Each patient will remain within the study for at least 1 year. All patients will continue active treatment within the study until the last patient recruited has completed their 1 year's active treatment, meaning that the first patient recruited will remain on active treatment for approximately 2 years in total. Patients can withdraw at any point, and such incidences will be included within the quality of life analysis.

Primary Research Question

Is there a quality of life benefit from home oxygen therapy given as either long term daytime or nocturnal oxygen therapy compared with best medical therapy in patients with stable severely symptomatic chronic heart failure?

Primary Objectives

 To assess the quality of life benefits of home oxygen therapy in the management of patients with stable CHF who are still severely symptomatic despite maximally tolerated medical therapy.

Secondary Objectives

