4.4 Trial Timeline

Setup - 3 months (1 April 2011 – 30 June 2011)

IRAS approvals (MREC & CSP)
Completion of any additional licensing & approvals
Start 3 & 6 monthly TMG, TSC & DMEC cycles
Update and establish trial materials & database
Train centre teams
Start of systematic health economic review
Development of preliminary cost-effectiveness model

Recruitment - 12 months (1 July 2011 – 30 June 2012)

Commence patient recruitment and data collection Monitor and support patient recruitment and retention Launch and complete Qualitative & Oxygen sub studies

Follow Up - 24 months (ends 30 June 2013)

Maintain data collection at centres.

Address data problems that arise to avoid delays to subsequent stages.

Analyse and present initial Qualitative and Oxygen sub study findings.

Data Cleaning - 3 months (1 July – 30 September 2013)

Analysis - 3 months (1 October 2013 – 31 December 2013)

Write Up of Trial Report - 3 months (1 January – 31 March 2013)

Submission of HTA Draft Report – 14 days (15 April 2014)

Publish findings for the Main study, Qualitative and Oxygen sub studies.

5. Patient Eligibility and Participation

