5.3 Entry Procedures

Eligible patients will be approached in CHF, cardiology or general medical clinics. Patients may also be identified through eligible patient lists held at NHS GP practices (Patient Identification Centres), or via existing lists of likely eligible patients held within NHS Hospitals, and introduced to the trial by letter. They will be introduced to the study by a member of the local clinical or research team, usually the clinician responsible for their treatment (usually a consultant cardiologist), and have the opportunity to discuss the trial fully with both the clinician and the research nurse. Each participant will be informed of the aims, methods, anticipated benefits, potential hazards and discomforts of the study, both through the Patient Information Sheet (PIS) and verbally. The participant's right not to participate and the right to withdraw at any time, without the need to give an explanation and without detriment to their overall treatment will be clearly stated. Patients will have at least 24 hours between

receiving the Patient Information Sheet (PIS) and giving their informed consent. Confirmation of the written informed consent may then be taken by clinicians or suitably qualified nurses according to local practice.

Transport will be provided for patients, or transport costs paid according to preference. Patients will be recruited and followed up through the existing routine ongoing 6 monthly clinics. Most of the clinical assessments are routine, meaning the patient would undergo them whether they were in the trial or not. The three month assessments will normally be carried out in the participant's home, depending on patient preference. The final data collection (at the completion of the trial) will use the existing patient notes, so will not require a clinic or home visit.

All consent forms will be stored in accordance with local requirements and copies given to the participant, entered into the patient's hospital notes and kept in the site study file. Patient entry will be logged on-line with the York Trials Unit, who will allocate the patients trial number and also the arm to which they are randomised.

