5.6 Trial Completion

The trial will complete after the last patient has completed their final clinic assessment. This should occur 27 months after trial launch, and 24 months after the first patient is recruited. Participants will also have the opportunity to request continuation of HOT if they found this beneficial. Otherwise, HOT will be removed from the patient's home by the local oxygen supplier.

6. Trial Evaluations

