6.5 Health Economic Assessments

In addition to the EQ5D

Health Service Use Questionnaire

The Health Service Use Questionnaire is designed to measure the level of health service resource use. Respondents are asked to recall the amount of use they have made of the specified services over the previous 6 months.

[figure not shown]
Table 1: HOT Main Trial - Patient Assessment Schedule

Assessment	Months After Recruitment ¹							
	Baseline	3	6	12	18	24		
Clinical	Clinic	Home	Clinic	Clinic	Clinic	Clinic		
Age, Sex, Aetiology, Height	X							
Weight	Х		Х	X	Х	Х		
Current Medication	Х	X	Х	X	Х	Х		
Resting Pulse Rate & Blood Pressure, Respiratory Rate	Х	X	Х	X	Х	Х		
Assessment of Peripheral Oedema & Lung Crackles	Х		X	Х	X	Х		
ECG	Х		X	Х	X	Х		
Blood Test - BCP, FBC (Standard Biochem' & Haem')	Х		X	Х	X	Х		
Blood Test – Nt pro BNP	X ²	X	X	X	X	X		
Spirometry	X			Х		Х		
Echocardiogram	X			X		X		
6 Minute Walk Test & Pre/Post O2 Saturation	X		X	X	X	X		
Overnight Sleep Test (if locally accessible)	X		X	X	X	X		
Charlson Co-Morbidity Index	X		X	X	X	X		
Karnofsky Performance Score	X	X	X	X	X	X		
Quality of Life								
Minnesota Living with Heart Failure Questionnaire (MLWHF)	X	X	X	X	X	X		
Numerical Rating Scale - Breathlessness (NRS)	X	X	X	X	X	X		
Hospital Anxiety & Depression Scale (HADS)	X		X	X	X	X		
Epworth Sleep Score	X	X	X	X	X	X		
Health Economics								
EuroQoL	X		X	X	X	X		
Health Service Use Questionnaire (not all questions)	X		X	X	X	X		

.

¹ It is intended that all patients will participate in the trial for 12 months, or until the last patient has completed, up to a maximum of 24 months. Assessments occur at 3 months (+/- 7 days), or at 6 monthly time points (+/- 14 days) thereafter. At trial end summary data on mortality and hospitalisations will be collected from clinical records for all participants.

² Investigations in 'blue' are trial investigations. Those in 'black' are routinely used within clinics for this patient group.

7. Economic Analysis and Modelling

Systematic reviews will be conducted to identify existing studies providing information on the costs, resource use and health outcomes associated with CHF and HOT. The analysis will be undertaken from the cost perspective of the NHS and using methods outlined in the National Institute of Health and Clinical Excellence (NICE) methods quide.xii

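### Adverse-event reporting closes 30 days after each patient's last clinic while trial oxygen runs on to a common end date, leaving roughly 9–13% of scheduled oxygen exposure outside the reporting period

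*Protocol*

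**What the plan says.** - **AE window (section 9.2):** reporting starts at randomisation "and ends 30 days after the patients' final research clinic appointment". AEs are elicited by asking patients at visits.
- **Treatment period (section 1):** "All patients will continue active treatment within the study until the last patient recruited has completed their 1 year's active treatment". As a result, "the first patient recruited will remain on active treatment for approximately 2 years in total".
- **Visits (Table 1):** a home visit at 3 months, then clinics at 6, 12, 18 and 24 months, counted from each patient's own recruitment. Footnote 1 allows 14 days either side of the 6-monthly visits.
- **Closing data collection (section 5.3):** it "will use the existing patient notes, so will not require a clinic or home visit". Table 1, footnote 1, adds: "At trial end summary data on mortality and hospitalisations will be collected from clinical records for all participants". Section 6.1 likewise takes closing data from hospital records.
- **Dates:** section 4.4 gives "Recruitment - 12 months (1 July 2011 – 30 June 2012"). Section 5.6 says of trial completion: "This should occur 27 months after trial launch, and 24 months after the first patient is recruited".

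**The concern.** Two clocks are in use. Treatment ends on one calendar date for everyone. Clinics, and with them the AE window, follow each patient's own entry date. No closing visit joins the two, so a patient whose entry date puts trial end between 6-monthly marks stays on trial oxygen after the last scheduled clinic, in most cases for more than 30 days.

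Section 2 cites reports of adverse haemodynamic effects of hyperoxia, says that long-term oxygen has not been studied in heart failure, and notes that earlier nocturnal-oxygen trials followed patients for at most 3 months. Late exposure is therefore part of what this trial newly offers on safety, and it is late exposure that the window cuts off.

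The rule is also silent on patients who die or stop attending. Sites could read the final appointment as the last one scheduled or as the last one attended.

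**Working it through.** **1. The plan's own timeline.** Recruitment of 12 months plus 12 months for the last recruit gives 24 months from the first patient. Adding 3 months of setup gives 27. Both figures in section 5.6 reproduce.

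**2. One patient.** Entry one month into recruitment gives 24 − 1 = 23 months of treatment. The last scheduled clinic is at month 18. Thirty days is 30 / 30.44 = 0.986 month, so reporting closes at month 18.99 and about 4.0 months of trial treatment remain.

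**3. All patients.** Inputs from the Protocol are 12 months of recruitment, a common end at month 24, clinics every 6 months, and 450 patients allocated 1:1:1 (300 on oxygen). Assumptions are uniform entry, visits on nominal dates, and no deaths or withdrawals.

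- Treatment length is T = 24 − u, with u uniform on 0 to 12, so mean T is 18 months.
- Time from last clinic to trial end, r, is uniform on 0 to 6 months.
- Share of patients with some uncovered time: (6 − 0.986) / 6 = 0.836, about 84%.
- Mean uncovered time: (6 − 0.986)² / (2 × 6) = 5.014² / 12 = 2.10 months. The maximum is 5.0 months.
- Share of scheduled exposure: 2.095 / 18 = 11.6%.
- Oxygen arms: 300 × 2.095 = 629 of 300 × 18 = 5,400 patient-months, or about 52 of 450 patient-years.

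**4. Sensitivity to the assumptions.**

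| Assumption changed | Uncovered share |
|---|---|
| Base case (uniform entry) | 11.6% |
| Entry density rising linearly over the year | 10.2% |
| Entry density falling linearly over the year | 12.8% |
| Assumed 1-year mortality 10% / 20% / 30% | 10.8% / 9.9% / 9.0% |
| Patients within 14 days of their next clinic at trial end attend it early | 9.6% |

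For the last row, a 6-month interval is 182.6 days. Only r between 30 and 168.6 days is then uncovered, so the mean is 138.6² / (2 × 182.6) = 52.6 days, or 1.73 months, and 1.73 / 18 = 9.6%. Affected patients fall to 138.6 / 182.6 = 76%.

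**5. Deaths, under each reading of the final appointment.** With the same assumed 1-year mortality of 10–30%:

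- Last scheduled clinic: about 9–11% of deaths fall after the window.
- Last clinic attended before death: 80–81% would, or 74–75% if the 3-month home visit counts.

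**6. What the gap loses.** The trial-end records review counts deaths and admissions for everyone. Sections 9.1 and 9.3 also class as serious some events that need involve neither, such as life-threatening events, lasting disability, and medically significant events treated at home or in an emergency room. Those events, and all non-serious ones, have no planned capture after the window. Nor is a form or a relatedness judgement required there for the deaths and admissions that are counted.

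**The case against.** **Most deaths escape safety reporting.** A reader might infer this from the 80% figure above. The Protocol does not support it. That reading closes, in retrospect, a window that was open on the day of the event, when no site could know that no later clinic would be held. On the ordinary reading the figure is about 9–11%. What stands is that the wording states no rule for these patients.

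**Late serious events go uncollected.** A reader might infer this too. It is wrong for deaths and admissions, which are taken from records for all participants. Mortality and days alive and out of hospital are secondary endpoints in section 3.5.

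**Other routes remain open.** Section 9.3 triggers the 15-day report when the chief investigator becomes aware of a related and unexpected event, and sets no cut-off of its own. Section 10.4 records AEs as the trial runs. The flow chart in section 4.1 ends with an assessment for further NHS oxygen, so there may be patient contact near the end. This is fair: a late event that comes to notice could still be reported. But none of these provisions requires AEs to be sought or assessed after the window closes.

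**The gap is the same in every arm.** This stands. It depends on entry date, which randomisation balances, so it shortens late safety follow-up without biasing the comparison.

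**The 12% is soft.** This also stands. It describes scheduled exposure, not hours of oxygen used, and rests on the assumptions listed. The range should be quoted with it.

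**Conclusion.** The end of the AE window and the end of trial treatment do not match, and the stated rule itself produces the gap. With uniform entry, nominal visit dates and no attrition, about 84% of patients have treatment time outside AE reporting, averaging about 2.1 months, or about 12% of scheduled oxygen exposure. Varying the entry pattern, mortality or use of the visit window gives roughly 9–13%.

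The loss is limited to forms, relatedness and expectedness assessment, non-serious events, and serious events without admission. It leaves the primary quality-of-life analysis and the counting of deaths and admissions untouched. The missing rule for deaths and missed clinics is a separate ambiguity in the same sentence. The change is worth making because it is cheap and concerns the late exposure that earlier trials did not observe.

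**What to change.** Reconcile sections 1, 5.6, 6.1, Table 1 and 9.2, and reword the end of the window in 9.2 along these lines:

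- AE reporting ends 30 days after the end of the patient's trial participation (the common trial end date, or earlier withdrawal of consent), or at death.
- Missed clinics do not close the window.
- Oxygen continued on the NHS after trial end is not trial treatment, so it does not extend the window.

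Add AE/SAE extraction, with relatedness assessment, to the trial-end notes review already planned in sections 5.3 and 6.1. With the window reworded, the share of trial treatment outside it falls to zero.

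The cost is a few more SAE forms per site and about 30 days of AE collection running into the data-cleaning period that starts on 1 July 2013. Recovery will be partial, because notes will show only some of the events that did not reach hospital. No treatment rule changes.

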9.3 Recording and Reporting Instructions

Each AE will be classified by the investigator as SERIOUS or NONSERIOUS and should be recorded on the 'serious adverse event form' or 'non serious adverse event form'.

An adverse event is defined as being serious if it is an untoward occurrence that:

- (a) results in death,
- (b) is life-threatening,
- (c) requires hospitalisation or prolongation of existing hospitalisation,
- (d) results in persistent or significant disability or incapacity.
- (e) consists of a congenital anomaly or birth defect, or
- (f) is otherwise considered medically significant by the investigator

If a research participant experiences an adverse event which in the opinion of the chief investigator is both

- 'related': that is, it resulted from administration of any of the research procedures;
 and
- 'unexpected': that is, the type of event is not listed in the protocol as an expected occurrence.

Then it will be reported to the Research Ethics Committee that gave a favourable opinion of the study and the sponsor (Hull and East Yorkshire Hospitals NHS Trust R&D department) within 15 days of the CI becoming aware of the event using the NRES safety report form available from:

http://www.nres.npsa.nhs.uk/applications/after-ethical-review/safetyreports/safety-reports-for-all-other-research/#safetynonCTIMPrepotingSAEs

9.4 Annual Progress Reports

An annual progress report will be submitted to the main REC which gave the favourable opinion 12 months after the date on which the favourable opinion was given and thereafter until the end of the study according to the NRES website below:

http://www.nres.npsa.nhs.uk/applications/after-ethical-review/annual-progress-reports/

10. Research Governance

The Neon Trial was approved by the HTA for funding on 31 March 2008(HTA Ref 06/80/01), and by the Northern and Yorkshire Multi Centre Research Ethics Committee on 24 August 2009 (Ref: 09/H0903/41).. The trial was substantially revised, renamed 'HOT' and approved by MREC on 18 May 2011. A non substantial amendment addressed minor issues on 15 May 2012.

10.1 Study Organisation Structures & Responsibilities

The sponsor of the trial will be Hull and East Yorkshire NHS Trust. The trial will be managed by the University of York Trials Unit, on behalf of [name] (Chief Investigator).

Chief Investigator - The Chief Investigator will have overall responsibility for the design, coordination and management of the study. These include:

- Trial authorization including responsibility for the protocol, obtaining approvals from MREC
- Ensuring that the trial is conducted according to Good Clinical Practice (GCP)
- Assessment of SAEs and providing a prompt response as to whether the SAE is a SUSAR.

Trial Manager The trial manager will be directly responsible to the Chief Investigator for liaison between the HTA, Hull and East Yorkshire NHS Trust, York TU, the Hull-York Medical School, the Comprehensive Local Research Networks, local project teams, and other parties as required. Duties include;

- Coordination of the components of the trial
- Initial start up and ongoing assistance with centres
- Financial management
- Reporting

Clinical Trials Unit – The Chief Investigator has delegated the responsibility for overall project management, data management, monitoring and ongoing statistical support to the York TU. Responsibilities include:

- Assistance with completion of the NRES form and communication with MREC
- Production of trial specific documentation (i.e. CRFs)
- Assistance with SSA procedures within centres
- Facilitating set up of trial centres
- Data management
- Responding to centre queries
- Pharmacovigilance Reporting of SAEs / SUSARs

Statistical Analysis – [name], employed by the Hull-York Medical School, and based within the Department of Health Sciences, University of York, will undertake the final analysis arising from this study.

The Principal Investigator at each participating centre will be responsible for obtaining local site-specific assessment (SSA) approval, and for the local conduct of the study. All correspondence relating to research ethics committees should be filed and maintained by the Investigator at each site.

Local Project Teams – These will consist of consultants, usually **Cardiologists** (responsible for introducing the patient to the trial and ensuring eligibility and consent) and **Research Nurses or other suitably qualified nurses** (responsible for patient recruitment, obtaining consent, and co-ordination of all aspects of data collection). Centres are specifically responsible for conducting the trial in accordance with the protocol, standard operating procedures (SOPs), trial agreement and MRC-GCP of both the trial and local practice.

10.2 Trial Management, Monitoring and Oversight

Data Monitoring and Ethics Committee (DMEC) – The DMEC will normally review the safety and ethics of the trial by reviewing interim data every 6 months. The terms of reference of the Data Monitoring and Ethics Committee are to:

- Ensure that patient considerations are of prime importance.
- To review any safety issues arising during the trial (including any SAEs and SUSARs).
- To report (following each DMEC meeting) its recommendations regarding trial continuation to the Trial Steering Committee.
- To consider any requests for release of interim trial data and to make recommendations to the Trial Steering Committee on the advisability of this.
- Should data summaries be required during the study, to provide to the Trial Steering Committee appropriate information and advice on the data gathered to date that will not jeopardize the integrity of the study.

Trial Steering Committee (TSC) – The TSC will provide overall supervision of the trial, in particular trial progress, adherence to protocol, patient safety and consideration of new information. An independent chair has been appointed and all co-applicants are members. The Committee will normally meet every 6 months. The terms of reference of the Trial Steering Committee are as follows:

- To provide overall supervision of the trial, ensuring adherence to protocol.
- To review developments during the trial and recommend appropriate action.
- To ensure that the rights, safety and well being of trial participants is safeguarded and prioritized.

Trial Management Group (TMG) - The TMG will comprise of the Chief Investigator, other lead investigators (clinical and non-clinical), members with a specific interest (e.g. nurses; patient representatives) and members of York TU. The TMG will be responsible for the day-to-day running and management of the trial and will meet approximately every six months for the duration of the trial. The terms of reference of the Trial Management Group are as follows:

• Be responsible for the day-to-day running of the trial.

Be responsible for the management of the trial

Data Monitoring

York TU will monitor receipt of CRFs and evaluate incoming CRFs for compliance with the protocol, inconsistencies and missing data. Participating centres may be monitored by York TU to confirm compliance with the protocol and complete source data verification (SDV).

